9.7.2.1 Missing or Incomplete Data and Loss to Follow-up

The eCRFs will be designed to minimize missing data and to optimize the integrity of collected data. Patients' records will not be excluded because of missing data but will be recorded for as missing if a specific covariate is not available for evaluation. The proportion of missing data will be reported for each measured variable in the study. Since data is collected from medical charts led as per standard of care, it is expected that data will be reasonably complete, however some missing data can also be expected.

A patient will be considered lost to follow-up if he or she is unable to be contacted by the study site for completion of questionnaire.

The following actions must be taken if a patient is unable to be contacted by the study site:

- The site must attempt to contact the patient as soon as possible and counsel the patient on the importance of completing the questionnaire and ascertain whether or not the patient wishes to and/or is able to continue in the study.
- In cases in which the patient is deemed lost to follow-up, the investigator or designee must make every effort to regain contact with the patient (where possible, 3 telephone calls and, if necessary, a certified letter to the patient's last known mailing address or local equivalent methods). These contact attempts are to be documented in the patient's medical record.
- If the patient continues to be unreachable, he/she will be considered to have withdrawn from the study with a primary reason of lost to follow-up.
- For patients who are lost to follow-up, the investigator can search publicly available records (where permitted) to ascertain survival status. This ensures that the data set(s) produced as an outcome of the study is/are as comprehensive as possible.

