9.2.5 Study Follow-up

This is a prospective study where data will be collected at routine clinical visits which will occur per standard of care (for a period of up to 12 years). A total of 12 years follow-up or 144 months of follow-up is planned for study 20180130. At each data collection stage, relevant information will be retrieved from patient charts subsequent to the preceding data abstraction time point to ensure there is no gap in data collection. Data abstraction will be performed approximately every 6 months (± 30 days) starting at enrolment. Additional data on neuropsychomotor development will be assessed through specific questionnaires (paper and/or electronic) which will be administered at pre-specified intervals starting from enrolment (approximately every 6 months [± 30 days] for patients up to 6 years old and approximately yearly [± 60 days] for patients from 6 years old). For each enrolled patient, data collection will end at 12-years of follow-up, the age of 25 years, loss-to-follow-up, withdrawal of consent, or death, whichever occurs earliest. All treatments for ALL will be captured in this period.

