9.6 Data Management

All data will be entered by sites into an eCRF that will be used to build the study database. Data abstraction will be done approximately every 6 months $(\pm 30 \text{ days})$ starting from enrolment. Additional data on neuropsychomotor development will be assessed through specific questionnaires (paper and/or electronic) which will be administered at pre-specified intervals starting at enrolment (approximately every 6 months [± 30 days] for patients up to 6 years old and approximately yearly [± 60 days] for patients from 6 years old) either in person or via telephone interview or mail. The score and percentiles from the questionnaires will be used for the final analysis. The final analysis cohort will be constructed from the complete review of inputted data documenting events in a patient's history from primary disease diagnosis until the earliest occurrence of the following events: death, withdrawal of consent, end of available data in the chart, completion of the 12-year follow-up period, or up to the age of 25 years. Data to be abstracted include variables relating to ALL diagnosis, ALL-associated treatment, development impairment, HSCT-associated AEs, leukemia relapse, long-term AEs, secondary malignancy until the earliest of: death, withdrawal of consent, end of available data in the chart, completion of the 12-year follow-up period, or 25 years of age.

Each patient will be assigned a unique identification number at the time of the first data entry. This unique identification number will be used to link data to subsequent data entries. The data will be abstracted by site staff from patient medical records into a web-based electronic data capture (EDC) system, using an electronic abstraction form that will provide an integrated, transparent tool to facilitate and record center recruitment, case identification, patient selection and study progress at the center and patient level.

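### Questionnaire non-contact counts as loss to follow-up and ends all data collection under Sections 9.2.1, 9.2.5 and 9.7.2.1, while Section 9.6 runs to the end of the chart, so one patient can have two end dates

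*Protocol*

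**What the plan says.** Two sets of stopping rules appear in the protocol.

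- **Section 9.7.2.1** sets a single trigger, under which a patient counts as "lost to follow-up if he or she is unable to be contacted by the study site for completion of questionnaire". Sites must then try to regain contact ("where possible, 3 telephone calls and, if necessary, a certified letter") and document the attempts. If these fail, "he/she will be considered to have withdrawn from the study with a primary reason of lost to follow-up". The only later data source named is for vital status: "the investigator can search publicly available records (where permitted) to ascertain survival status".
- **Section 9.2.5** says that "data collection will end at 12-years of follow-up, the age of 25 years, loss-to-follow-up, withdrawal of consent, or death, whichever occurs earliest". The abstract (Section 4) and Section 9.2.1 also end follow-up at loss to follow-up. None of these makes an exception for chart abstraction.
- **Section 9.6** says that the final analysis cohort runs to the earliest of "death, withdrawal of consent, end of available data in the chart, completion of the 12-year follow-up period", or age 25. It gives the same set of end points again for the data to be abstracted. Loss to follow-up is in neither list.

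Sections 9.2.5 and 9.4 describe chart review as its own 6-monthly stream. The neuropsychomotor questionnaires are described as additional to it.

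**The concern.** Failure to reach a family for a questionnaire says nothing direct about whether the site's chart is still being filled. The questionnaires named in Section 9.3.1 (Vineland-3 and BRIEF) measure neuropsychomotor development. The protocol names no questionnaire for the other three primary domains (neurological, endocrine, immune), nor for relapse or second malignancy. Yet under Sections 9.2.5 and 9.7.2.1 non-contact stops all of these together.

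Three things are at stake:

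- **An undefined end date.** Sections 9.7.2 and 9.7.2.2.3 plan Kaplan-Meier and Cox analyses. The two rules give different censoring dates for the same patient.
- **Late person-time.** Section 7.2 justifies the study by what is unknown beyond 3 years. Non-contact accumulates with time, so it removes late follow-up most.
- **Possible informative censoring.** Whether a family can be reached could depend on the child's condition.

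This is a collection rule. A statistical analysis plan can choose a censoring date, but it cannot recover data that sites were told to stop abstracting.

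**Working it through.** **Step 1: compare the end-of-data events.**

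| Event | Sections 4, 9.2.1, 9.2.5 | Section 9.6 (cohort and abstraction) |
|---|---|---|
| Death | yes | yes |
| Withdrawal of consent | yes | yes |
| 12 years | yes | yes |
| Age 25 | yes | yes |
| Loss to follow-up | yes | not listed |
| End of chart data | not listed | yes |

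Consider a patient who cannot be reached for the year-4 questionnaire and whose chart has entries to year 9. The first rule ends data at about year 4, the second at year 9.

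**Step 2: can withdrawal of consent in Section 9.6 absorb these patients?** Not cleanly. Section 9.7.2.1 records their reason as lost to follow-up. Sections 4, 9.2.1 and 9.2.5 list loss to follow-up separately from withdrawal of consent. Section 10.4 defines withdrawal of consent as not wishing, or not being able, to continue, and does not mention being unreachable.

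**Step 3: illustrate the size.** The protocol states no figure for non-contact, so there is none to reproduce. Inputs:

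- Annual non-contact rate *r* = 2%, 5%, 8%: assumed.
- Horizon 12 years: Section 9.2.5.
- Long-term survival 35%: Section 9.5. Placing it at 12 years with a constant hazard is an assumption, because Section 9.5 gives no time point.

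Mortality hazard: *m* = −ln(0.35)/12 = 0.0875 per year. Non-contact hazard: *h* = −ln(1 − *r*) = 0.0202, 0.0513, 0.0834.

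Share cut off by non-contact before death or 12 years = *h*/(*h* + *m*) × [1 − 0.35 × (1 − *r*)^12].

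- 2%: 0.188 × 0.725 = 0.136, about 14%
- 5%: 0.370 × 0.811 = 0.300, about 30%
- 8%: 0.488 × 0.871 = 0.425, about 43%

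Mean person-time without non-contact = (1 − 0.35)/*m* = 7.43 years. With non-contact it is [1 − 0.35 × (1 − *r*)^12]/(*h* + *m*).

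- 2%: 6.74 years, loss 1 − 6.74/7.43 = about 9%
- 5%: 5.84 years, loss about 21%
- 8%: 5.10 years, loss about 31%

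**Step 4: sensitivity to when deaths occur.** If all deaths fall in the first 3 years, the share cut off is about 9%, 20% and 28%. If deaths are ignored, 1 − (1 − *r*)^12 gives 22%, 46% and 63%. That last set contradicts the protocol's own survival assumption and should not be used.

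**The case against.** The strongest reply has five parts.

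1. **Withdrawal is a last step.** A reader might infer that one missed questionnaire removes a patient. The text does not support that: Section 9.7.2.1 requires prompt contact, counselling and documented repeat attempts first. Questionnaires may also be done in person, by telephone or by mail (Section 9.4), so a family that still attends the site can usually be reached. This stands, and it narrows the affected group. One loose end remains: the opening sentence already calls the patient lost before those attempts.
2. **Survival is not simply discarded.** A reader might infer that it is. Section 9.7.2.1 allows a public-records search for survival status, and Section 10.4 keeps data up to withdrawal of consent and allows public data afterwards. This stands, although the search is optional and only where permitted, and no other outcome has such a fallback.
3. **The lost chart time may not exist.** A patient who cannot be reached by telephone or letter may have left the site, so both rules would give nearly the same date. Section 9.9 already notes gaps when care is given elsewhere. The age-25 limit and the censoring of events after relapse or second malignancy (Section 9.7.2.2.3) reduce the usable time further. This stands. The documents do not support a claim that following Section 9.6 would keep most of the loss.
4. **Informativeness is not shown.** A reader might infer that the censoring is probably informative. Section 9.9 acknowledges bias if information is not missing at random, but nothing in the protocol shows that non-contact depends on outcome. It is a possibility only.
5. **Section 9.6 may only describe how the cohort is built from data already entered.** This fails, because the section applies the same end points to the data to be abstracted, which is a collection rule.

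**Conclusion.** The point holds as a contradiction in the protocol with a real but unquantified consequence. Sections 4, 9.2.1, 9.2.5 and 9.7.2.1 end all collection when a patient cannot be reached for the questionnaire. Section 9.6 carries on to the end of the chart. Following the first set would stop chart-based neurological, endocrine, immune, relapse and second-malignancy data for a reason unrelated to chart availability.

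The actual size is unknown. The illustration gives 14%, 30% and 43% of patients cut off and 9%, 21% and 31% of person-time lost. It rests on assumed non-contact rates of 2%, 5% and 8% a year and on constant mortality to 35% survival at 12 years. Under those assumptions the figures are upper bounds on what continued abstraction could recover, because some unreachable patients will have left the site and the age-25 limit shortens follow-up. Earlier deaths would lower the share cut off.

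This should be corrected. It does not invalidate the design.

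**What to change.** - In Section 9.7.2.1, let questionnaire non-contact end only the questionnaire component. Record it separately from loss of chart follow-up.
- Continue 6-monthly chart abstraction, where consent and local rules allow, to the end points in Section 9.6.
- Censor chart-based endpoints at the last chart entry.
- Use one list of end-of-data events in the abstract and in Sections 9.2.1, 9.2.5, 9.6 and 9.7.2.1.

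The cost is mostly wording. Sites would go on abstracting charts for patients they can no longer contact, and some countries may need consent or ethics text to cover that.

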9.7.2.2 Descriptive Analysis

Continuous variables will be summarized by mean, median, standard deviation, lower and upper quartiles, and minimum and maximum values. Categorical variables will be summarized by number and percentage of patients in each category. For categorical outcomes, 95% CIs will also be presented where appropriate.

9.7.2.2.1 Description of Study Enrolment

Study reporting period, patient number by country and site, and patient number overall and by analysis sets will be tabulated.

9.7.2.2.2 Description of Patient Characteristics

The study population will be characterized by patient and clinical characteristics (eg, age, sex, disease status, prior treatments) including the variables listed above.

9.7.2.2.3 Analysis of the Primary and Secondary Endpoints

Patient incidence proportions (and 95% Cls) for each of the specified outcome events will be summarized. KM estimates for time to first onset of each specified event will be provided.

For the events of interest, events that occur after a relapse or secondary malignancy will be censored as it is unlikely that events that occur after relapsed and treatment for relapse could be considered related to initial chemotherapy or blinatumomab treatment for the prior disease occurrence.

A comparison between the blinatumomab versus chemotherapy group will be conducted at the final follow-up in the study pending adequate sample size is enrolled $(\geq 50 \text{ patients per arm})$ and the blinatumomab and SOC groups are comparable (eg. there is overlap between PS distributions across the two groups, or no critical differences that cannot be accounted/adjusted for). Prior to comparison being conducted, covariates listed in Section 9.3.2 will be evaluated for differences between the two groups. Any covariates that are not comparable between the two (Wald chi-square or t-test, p-value < 0.25), will be evaluated as a covariate for adjustment in the models. The primary and secondary endpoint of discrete events (eg, incidence endpoints) will be compared by a logistic regression which will generate an odds ratio and 95% confidence interval of the odds of developing an event. Endpoints that are time-to-event will be compared by a Cox regression model which will generate hazard ratio and 95% confidence interval for the risk of developing an event. Also, we will additionally conduct a propensity score weighting analysis based on the covariates collected for this study. An additional sensitivity analysis may be done to adjust for the drop-in effect of patients receiving anti-cancer medications during follow-up.

A literature review of published data at the time of the final study report will be performed for the relevant endpoints. If there is any relevant scientific data publicly available by the time when the study ends (> 12 years later), Amgen will provide a comparative analysis. If a sufficient number of patients are identified in publicly available database with information on relevant confounding factors, Amgen will conduct a direct comparative analysis, but descriptive analyses will be undertaken either way.

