- Toxicity (gastrointestinal, hematologic, dermatologic, cardiac,

pulmonary, hepatic, renal, infection, skeletal, etc.)

Other important clinical factors

- Comorbidity
- Concomitant medication

- Prenatal development
- High-risk pregnancy
- Delivery complications including hypoxia
- Gestational time at the delivery
- APGAR score
- Gestational weight (IUGR)
- Psychomotor development impairment and psychiatric conditions recognised prior to the therapy
- Pregnancy and breastfeeding status after blinatumomab initiation
- Study Sample Size

The targeted sample size for this study is approximately 298 patients. However, the actual number of patients that will be included in the study will depend on the results of site feasibility, willingness of patients (or their legal guardians/caregiver) or sites to participate in the study.

• Data Analysis

Continuous variables will be summarized by mean, median, standard deviation, lower and upper quartiles, and minimum and maximum values. Categorical variables will be summarized by number and percentage of patients in each category. For categorical outcomes, 95% confidence intervals (CIs) will also be presented where appropriate. For time-to-event endpoints, Kaplan-Meier (KM) curves and KM proportions at select time points, the numbers of patients with events and then number of patients censored will be used to summarize the data.

A comparison between the blinatumomab versus chemotherapy group will be conducted at the final follow-up in the study pending adequate sample size is enrolled (\geq 50 patients per arm) and the blinatumomab and SOC groups are comparable (eg, there is overlap between PS distributions across the two groups, or no critical differences that cannot be accounted/adjusted for). Prior to comparison being conducted, covariates listed in Section 9.3.2 will be evaluated for differences between the two groups. Any covariates that are not comparable between the two (Wald chi-square or t-test, p-value < 0.25), will be evaluated as a covariate for adjustment in the models. A multivariate logistic regression will be used to compare incidence event objectives and Cox regression will be used to compare time-to-event objectives. Also, we will conduct a propensity score weighting analysis based on the covariates collected for this study.

This study will have 5 interim analyses, taken at 2-year intervals over the course of the 12-year follow-up. A final report will be produced at the end of the study.

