7.3 Statistical Inference

The study will compare blinatumomab therapy versus chemotherapy for the occurrence of neuropsychomotor developmental impairment, neurological impairment, endocrine impairment, and immune system impairment.

8. Research Question and Objectives

The overarching aim of this study is to describe and compare the long-term safety profile of B-precursor ALL paediatric patients who have been treated with either blinatumomab or chemotherapy prior to undergoing alloHSCT.

Primary 8.1

Primary Objective					
Objective	Endpoint				
 To estimate incidence of neuropsychomotor developmental impairment, endocrine impairment, neurological impairment, and immune system impairment (including auto-immune disorders and vaccine failure) 	 Impairment defined as any of the following: Neuropsychomotor development impairment in any area of social and emotional, language/communication, cognitive, or motor Neurologic impairment defined as any peripheral nervous system disorders including neuromuscular junction disorders; central nervous system disorders Endocrine impairment defined as any Hypothalamus-Pituitary-Gonadal Axis disorders; Hypothalamus-Pituitary-Adrenal (HPA) Axis disorders; Hypothalamus-Pituitary-Thyroid Axis disorders Immune system impairment defined as any leukopenia (neutropenia and/or lymphopenia); low IgG; low IgM, and; low IgA; autoimmune disorders; vaccination failure 				

8.2	Secondary
•	

• To estimate the incidence of Haemopoietic Stem Cell Transplant (HSCT) related adverse events (AEs)	 HSCT-related AEs defined as any second malignancy; Graft versus Host Disease (GvHD); infection, and/or; relapse
 To estimate the incidence of subsequent relapse of leukemia including in the central nervous system (CNS) 	 Relapse is defined as any of the following: Isolated bone marrow relapse (M3³ in the absence of extramedullary involvement) Combined bone marrow response (M2 or M3 marrow and at any extramedullary manifestation of ALL) Extramedullary relapse (either CNS relapse, testicular relapse, or relapse at other sites⁴)

³ Cytological bone marrow assessment grading: see Appendix F for details
 ⁴ See Appendix F for relapse criteria (including extramedullary relapse)

 To estimate the cumulative incidence of long-term AEs 	 AEs in any of the following organ systems: gastrointestinal, hematologic, dermatology, cardiac, pulmonary, hepatic, renal, neurological, infection, immunology, and skeletal

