9.5 Study Size

The targeted sample size for this study is approximately 298 patients. However, the actual number of patients that will be included in the study will depend on the results of site feasibility, willingness of patients (or their legal guardians/caregivers) or sites to participate in the study.

According to Marshall et al 2013, paediatric ALL patients are expected to have toxicity during intensification of therapy, generally related to hematological counts (Marshall et al, 2013). All patients also expect to have some immune complications after treatment end (Perkins et al, 2017) that will persist for some time.

Assuming that between 85%-98% of all patients will have at least one event, the expected ranges of sample sizes and relevant 95% CI is provided below. If 100 patients are enrolled.

95% C	onfidence	Interval o	of Estimated	Incidence o	of Adverse	Events by	Sample
-------	-----------	------------	--------------	-------------	------------	-----------	--------

S	ize	

Enrolled N Per Arm	Estimated Incidence of events	95% Confidence Interval*
150	98%	94.3%-99.3%
150	90%	84.1%-93.9%
150	85%	78.4%-89.8%
100	98%	93%-99.5%
100	90%	82.5%-94.5%
100	85%	76.7%-90.7%
75	98%	90.8%-99.3%
75	90%	82.0%-95.4%
75	85%	75.6%-91.6%
50	98%	89.5%-99.7%
50	90%	78.6%-95.7%
50	85%	71.5%-91.7%

* Wilson score interval

Sample size calculation for comparison analyses was calculated based on the number of long-term survivors needed. A risk difference of 10% (98% vs 88%) is considered as clinically significant. If the sample size is 52 long-term survivors per arm (104 in total), then a risk difference of as little as 10% will be detectable (p-value < 0.05).

Number of Long-term Survivors per Arm	Observed Risk Difference	P-value*
52/52	98% vs 88% = 10%	0.0455
40/40	98% vs 86% = 12%	0.0477
30/30	98% vs 83% = 15%	0.0477
20/20	98% vs 77% = 21%	0.0444

* z-test of two proportion comparison

Assuming a 35% long-term survival rate, the required number of patients entering the study per arm is 149 (52/0.35). Therefore, the number of patients entering the study needed to successfully fulfill the primary objectives while taking into account the 35% survival rate is 298.

Even though long-term survivors contribute the most essential data to this study, all enrolled patients contribute important information. If the total sample size is 149 patients per arm (298 in total), then a risk difference of as little as 5% will be detectable (p-value < 0.05).

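### Kaplan-Meier with relapse, second malignancy and death censored gives a hypothetical net risk, not the incidence that the objectives ask for

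*Protocol*

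**What the plan says.** The objectives are incidences. Section 8.1 asks for the incidence of four kinds of impairment. One secondary objective in section 8.2 reads "To estimate the cumulative incidence of long-term AEs".

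Section 9.7.2.2.3 fixes two estimators. The first is a crude proportion: "Patient incidence proportions (and 95% Cls) for each of the specified outcome events will be summarized". The second is Kaplan-Meier: "KM estimates for time to first onset of each specified event will be provided". The same section adds that "events that occur after a relapse or secondary malignancy will be censored", on the ground that later events are unlikely to reflect the initial treatment. Arms are compared by logistic regression for incidence endpoints and by Cox regression for time-to-event endpoints, if the comparison goes ahead.

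On death, section 9.2.5 says that "data collection will end at 12-years of follow-up, the age of 25 years, loss-to-follow-up, withdrawal of consent, or death, whichever occurs earliest". The data analysis part of the Abstract describes the time-to-event summary with two states only: "Kaplan-Meier (KM) curves and KM proportions at select time points, the numbers of patients with events and then number of patients censored". The protocol mentions neither competing risks nor a cumulative incidence function.

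On how often patients leave the risk set, section 9.5 sizes the study by "Assuming a 35% long-term survival rate". Section 7.1.2 reports a second relapse within 2 years in about 50% of patients with high-risk first relapse.

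**The concern.** Kaplan-Meier treats a censored patient as someone who could still have the event later, at the same rate as those who remain under observation. A patient who has died cannot. A patient who has relapsed is, under the protocol's own rule, no longer counted. Both are competing events. Censoring them makes 1-KM the risk that would apply if nobody died, relapsed or developed a second cancer. It is not the share of transplanted children who develop the impairment.

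At stake are the main absolute figures of a study that section 7.2 calls a category 1 regulatory commitment. Two incidence figures for the same outcome, the crude proportion and the KM figure, would stand side by side and disagree, with nothing to tell the reader which one answers the objective. The gap would be widest for outcomes that can appear late, such as endocrine and neuropsychomotor impairment.

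**Working it through.** **The protocol's own figure.** Section 9.5 needs 52 long-term survivors per arm and assumes 35% survival: 52 / 0.35 = 148.6, rounded up to 149 per arm, or 298 in total. This reproduces. The same 35% is used below.

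**Inputs**
- 35% remaining free of competing events at 12 years. *Assumption:* section 9.5 gives the 35% as long-term survival with no horizon, and relapse or second malignancy would remove further patients.
- 12 years of follow-up (section 9.2.5).
- 1-KM values of 85% and 98%: the section 9.5 range for patients with at least one event.
- 1-KM values of 20%, 30% and 50%: *assumption*, because the protocol gives no rates for individual late outcomes.
- Event and competing hazards independent of each other: *assumption*.

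**Formula, constant hazards.** With F = 1-KM at 12 years, the event hazard is a = -ln(1-F)/12. The competing hazard is c = -ln(0.35)/12 = 0.0875 per year. The cumulative incidence is

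CIF = a/(a+c) × (1 - exp(-12(a+c))).

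For F = 30%: a = 0.3567/12 = 0.0297 and a+c = 0.1172. Then CIF = 0.2536 × (1 - 0.245) = 19.1%, and the ratio is 30/19.1 = 1.57.

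**Sensitivity to timing.** Two variants bracket this case. In one, all competing losses fall in years 0-3 and the event hazard is constant over 12 years. In the other, all events fall in year 1 and the competing hazard is constant.

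| 1-KM | CIF, constant hazards (ratio) | CIF, losses in years 0-3 (ratio) | CIF, events in year 1 (ratio) |
|---|---|---|---|
| 20% | 12.6% (1.58) | 8.5% (2.35) | 19.2% (1.04) |
| 30% | 19.1% (1.57) | 12.8% (2.34) | 28.8% (1.04) |
| 50% | 32.8% (1.52) | 21.9% (2.28) | 48.1% (1.04) |
| 85% | 61.0% (1.39) | 40.9% (2.08) | 82.5% (1.03) |
| 98% | 78.3% (1.25) | 54.3% (1.80) | 96.0% (1.02) |

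A gentler front-loading, with 0.35 + 0.65 exp(-t/2) remaining at t years, gives CIFs of 9.3%, 14.1% and 24.2% for 1-KM of 20%, 30% and 50%. The ratios are 2.15, 2.13 and 2.07.

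**Arm comparison.** Give both arms the same event hazard (1-KM of 50%), but let 25% remain in one arm and 45% in the other (assumption). The CIFs are 29.2% and 36.0%. The odds ratio is (0.360/0.640) / (0.292/0.708) = 0.5625/0.4124 = 1.36, although the cause-specific hazard ratio is 1. The arm that loses fewer patients shows more events because its patients stay at risk longer.

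**The case against.** **The crude proportion is not wrong in itself.** A reader might infer that it understates incidence because it counts patients who die or relapse first as event-free. With complete follow-up it does not: it equals the Aalen-Johansen estimate with those events as competing. It runs low only through incomplete follow-up, that is, loss to follow-up, interim data cuts and the age-25 cap. Because 25 - 12 = 13, a patient transplanted after the 13th birthday cannot complete 12 years. This part of the objection stands.

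**The odds ratio is not an artefact that better curves would remove.** The 29.2% and 36.0% above are cumulative incidences, so Aalen-Johansen curves by arm would show the same difference. It is a real difference in absolute risk that mixes event hazard with survival and relapse. It has to be read beside the cause-specific hazard ratio.

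**Overall survival.** The heading of section 9.7.2.2.3 covers primary and secondary endpoints, so a reader might infer that deaths after relapse are censored from overall survival. The text does not support that firmly. The sentence is limited to events of interest, and its reason concerns attribution to the initial treatment. The Abstract defines survival as time from transplant to death, and follow-up does not stop at relapse. What remains is an undefined scope, which one clause would settle.

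**Deaths.** A reader might infer that 65% are expected to die by 12 years and that the protocol orders death to be censored. It states neither. The first needs a horizon that section 9.5 does not give. The second follows only from follow-up ending at death and from a summary with two states.

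**Part of the remedy is already planned.** A Cox model that censors at competing events is a cause-specific model. Leaving out post-relapse events is a reasoned choice. Both points stand, but neither turns 1-KM into an incidence.

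**Conclusion.** The point holds for 1-KM. The protocol itself fixes this method, so it is not a detail left to a SAP. KM that censors at relapse or second malignancy, and by implication at death, cannot deliver the incidence or cumulative incidence that the objectives name. Under the stated assumptions the overstatement under constant hazards is about 1.6-fold at 1-KM of 20-30%, 1.4-fold at 85% and 1.25-fold at 98%. It is roughly 2-fold for late events when losses come early, and 2-4% in relative terms for events confined to the first year. The size therefore depends on hazard shapes that the protocol does not give.

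The crude proportion and the Cox hazard ratio remain usable if they are read for what they are. The logistic odds ratio should not be read alone as a measure of toxicity. This should be fixed, but it does not undermine the design.

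**What to change.** 1. Report Aalen-Johansen cumulative incidence by arm at fixed times for each outcome. Treat death, relapse and second malignancy as competing events wherever they are not the outcome itself.
2. If 1-KM is kept, label it as a hypothetical net risk.
3. Describe the planned Cox models as cause-specific and make them the main comparison of event risk. Present the crude proportion and logistic odds ratio beside them, and report how complete follow-up was.
4. State how death is handled. Add a clause that the rule on events after relapse or second malignancy does not apply to overall survival, relapse or secondary malignancy.
5. Optional: a sensitivity analysis that counts events after relapse. Follow-up continues beyond relapse, so the data should exist.

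The cost is a few sentences in the protocol and standard software. No extra patients or data are needed. The reported incidences will be lower than 1-KM.
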